### **2.3. Safety Endpoints**

Except for infusion-related site reactions, the [National Institutes of Health Division of AIDS \(DAIDS\) Table for Grading the Severity of Adult and Pediatric Adverse Events, Corrected Version 2.1 \(July 2017\)](#) will be used to assess and grade AE severity, including laboratory abnormalities judged to be clinically significant.

Criteria for relatedness of adverse events is given Sec 11.1.2 of the study protocol. Criteria for SAE are given in Sec 11.2 of the protocol.

- Safety endpoints include number of participants with adverse events (AE)s (Treatment Emergent Adverse Events (TEAE)s, Serious Adverse Events (SAE)s, and Adverse Events of Special Interest (AESI). The primary outcome will be the number of individuals in each group experiencing a severe (Grade 3 or greater) AE thought to be possibly, probably, or definitely related to study treatment throughout the study duration. Specific AESI and their associated symptoms experienced with IV infusions include the following:
  - Immune-mediated AEs include Type I – Type IV hypersensitivity reactions. Types I-III occur within the first 24 hours of exposure and are considered immediate reactions. Type IV are considered delayed. They can occur up to 72 hours post exposure.
  - Type I hypersensitivity reactions manifest as anaphylaxis, urticaria, and angioedema.
  - Type II hypersensitivity reactions involve cell depletion and/or destruction without inflammation.
  - Type III hypersensitivity reactions involve immune complexes causing serum sickness type reactions.
  - Type IV hypersensitivity reactions are cell mediated inflammatory responses.
  - Cytokine release syndrome – may mimic anaphylaxis and present with hypotension, urticaria, and an overall hyperinflammatory response.

### **2.4. Sample Size and Study Power**

This is an exploratory study, and the primary results are meant to be descriptive. We use AER002 as a probe to better understand LC biology and determine whether a signal is present to warrant further study.

The study planned at least 30 participants who meet the WHO LC criteria. Participants are enrolled at a single center and randomized 2:1 to receive AER002 1200 mg or placebo.

For PROMIS-29, assuming a standard deviation (SD) of the within-person difference of 10, then the planned sample size has 80% power to detect a difference of 11.2 on a two-sided 0.05 level test.

For biomarkers, such as IL-6, we can detect a difference from a mean value of 2.5 pg/mL to 1.1 times the within-person standard deviation with 80% power.

### **3. Analysis Principles**

The following principles apply for the comparisons of the participants randomized to AER002 (“active group”) versus the participants randomized to placebo (“control group”).

#### **3.1. Analysis populations**

Comparisons for *safety and efficacy outcomes* will be by *modified intention-to-treat (mITT)*. The modified intention-to-treat analysis is restricted to participants who received any of the blinded AER002/placebo (full or partial infusion); participants who did not receive *any* AER002/placebo are excluded from the mITT population.

Sensitivity analyses by *intention-to-treat (ITT)* will be carried out for the primary efficacy outcome and key secondary outcomes. The ITT population is all participants who were randomized during the study and assigns them to the group to which they were randomized.

The *per protocol population (PP)* is restricted to participants who received any of the blinded AER002/placebo (full or partial infusion). It excludes participants who received a non-study COVID-neutralizing mAb during the trial period, anyone with resistant SARS-CoV-2 infections during the trial or receipt of COVID antivirals during the trial and recent acute illness.

The safety population will be identical to the mITT population.

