### **15.1 Data Sets Analyzed**

Eligible patients who are randomized into the study and receive the study drug will comprise the modified intent to treat (mITT) population and will be the primary analysis population for all analyses.

Per protocol analysis will be based on description of the results per study group excluding anyone who has received a non-study COVID-neutralizing mAb during the trial period, anyone with resistant SARS-CoV-2 infections during the trial or receipt of COVID antivirals during the trial.

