## 2. Study Design

### 2.1. Randomization and Follow-Up

This is an exploratory, 2:1 randomized, double-blind, placebo-controlled study to assess the safety and efficacy of AER002 to treat Long COVID (LC).

The study will enroll approximately 30 participants who meet the WHO LC criteria. Participants will be enrolled at a single center and randomized 2:1 to receive AER002 1200mg or placebo (20 to AER002 and 10 to placebo). Evaluations will take place at baseline and at timepoints up to 1-year post-infusion.

Screening data will be reviewed to determine subject eligibility. Subjects who meet all inclusion criteria and none of the exclusion criteria (see study protocol) will be entered into the study.

The following treatment regimens will be used:

Route	Planned Dose	Dose	mL	Total Dose	Total mL
Intravenous (IV)	AER002	1200 mg	24	1200 mg	24
	Placebo	NA	24	NA	24

The total duration of subject participation will be approximately 12 months. The study visits will occur at screening, baseline, infusion and days 15, 30, 90, 180 and 360 (D15, D30, D90, D180, D360, respectively) following infusion.

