### **3.8. Intercurrent Events**

Our analysis may be affected by SARS-CoV-2 reinfections during the study period. Our primary analysis will include all visits during the study period. We will perform sensitivity analyses which exclude any visits after a documented or suspected on study reinfections.

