## **4. Efficacy Analyses**

The primary efficacy analyses will be conducted in the mITT population. Analysis in the per protocol population will be considered a sensitivity analysis.

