### **4.1. Primary Efficacy Outcome**

The primary efficacy outcome is the change in PROMIS-29 Physical Health summary score from Baseline to D90. This will be analyzed from the mITT population using a linear regression model for follow-up PROMIS-29 with terms for the baseline value, randomized treatment – an analysis of covariance model (ANCOVA).

The significance of the treatment comparison will be given by a two-sided 0.05 level test for the randomized treatment term.

The mean PROMIS-29 Physical Health summary score to D90 can be calculated by marginalizing the ANCOVA model above.

Note, these estimates will differ from both taking the mean PROMIS-29 at the baseline and D90 timepoints. However, the ANCOVA estimate is more efficient.

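### The per-protocol set removes whole participants for events at any time in the trial, so its D90 check discards scores recorded before the event

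*Combined protocol and SAP*

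**What the plan says.** SAP 3.1 defines a single per-protocol population among participants who received any study infusion. "It excludes participants who received a non-study COVID-neutralizing mAb during the trial period", and it further removes "anyone with resistant SARS-CoV-2 infections during the trial or receipt of COVID antivirals during the trial and recent acute illness". Protocol 15.1 describes the per-protocol results as "excluding anyone who has received a non-study COVID-neutralizing mAb during the trial period" together with "anyone with resistant SARS-CoV-2 infections during the trial or receipt of COVID antivirals during the trial"; it has no acute-illness item. Both definitions act on the participant, and neither sets a cut-off at the visit being analysed.

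SAP 2.1 gives the period involved: "The total duration of subject participation will be approximately 12 months", with the last visit at D360. SAP 4 gives the set its role: "Analysis in the per protocol population will be considered a sensitivity analysis". SAP 4.1 fixes the main timepoint: "The primary efficacy outcome is the change in PROMIS-29 Physical Health summary score from Baseline to D90".

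SAP 3.8 describes a separate sensitivity analysis for reinfection, which will "exclude any visits after a documented or suspected on study reinfections". That one acts on visits.

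**The concern.** Take a participant who attends D90, completes PROMIS-29, and is given a COVID antiviral at month 10. The D90 score was recorded about seven months before the antiviral, yet under SAP 3.1 it leaves the D90 per-protocol comparison. The same happens with a non-study antibody or a resistant infection after D90.

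Two things are at stake. The first is precision: with 20 participants on AER002 and 10 on placebo, each D90 score lost unnecessarily counts. The second is selection. Membership of the D90 comparison depends on what happens after D90. The antiviral criterion is not restricted to acute infection, so a participant still unwell at D90 could receive an antiviral later and be removed. The documents do not say how often this would happen, but the rule allows it.

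A per-protocol analysis is meant to show whether the mITT result survives removal of contaminated data. If uncontaminated data go too, a difference from mITT is harder to read.

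**Working it through.** **Inputs.** From the SAP: 20 versus 10 participants (2.1); SD 10, difference 11.2, two-sided 0.05, 80% power (2.4); primary efficacy timepoint D90 (4.1); last visit D360 (2.1); D90 window ±14 days, so to D104, and an extended window to 4.5 months, about D135 (3.6). Protocol 9.1.9 expects some on-study infections but gives no rate. The incidence and timing of excluding events are therefore assumptions below.

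**1. The plan's own figure.** The standard error of the difference is 10 × √(1/20 + 1/10) = 3.873, so the noncentrality is 11.2 / 3.873 = 2.89. With 28 degrees of freedom a two-sample t-test has 79.7% power, and the difference detectable at 80% is 11.24. The stated figure reproduces. It is not in dispute and serves only to scale the loss.

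**2. Share of excluding events after D90.** Let c be the assumed cumulative incidence by D360, at a constant rate and equal in both arms. The proportion with an event by D90 is c90 = 1 − (1 − c)^(90/360), and the share of events after D90 is 1 − c90/c.

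**3. Precision.** As written, the D90 per-protocol set keeps 30(1 − c) participants. A rule limited to events before D90 keeps 30(1 − c90). The ratio of standard errors is √[(1 − c90)/(1 − c)].

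| Assumed c | c90 | Share after D90 | Lost as written | Lost if limited to D90 | SE ratio | Detectable difference, as written | Detectable difference, limited to D90 |
|---|---|---|---|---|---|---|---|
| 20% | 0.054 | 73% | 6 | 1.6 | 1.09 | 12.7 | 11.6 |
| 30% | 0.085 | 72% | 9 | 2.6 | 1.14 | 13.7 | 11.8 |
| 40% | 0.120 | 70% | 12 | 3.6 | 1.21 | 14.9 | 12.0 |

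Detectable differences are at 80% power with SD 10 and 2:1 allocation preserved.

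**4. Later D90 assessments.** For c from 10% to 50%, the share of events after D104 is 64% to 70%. After D135, the end of the extended window, it is 54% to 61%. Using D135 at c = 20%, 30% and 40%, the proportions with an event by then are 0.080, 0.125 and 0.174. The SE ratios become √(0.920/0.8) = 1.07, √(0.875/0.7) = 1.12 and √(0.826/0.6) = 1.17.

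**5. Early clustering.** Suppose the rate up to D90 is three times the later rate. Then 3 × 90 = 270 equals the remaining 270 days, so half the cumulative hazard falls before D90 and the event-free proportion at D90 is (1 − c)^(1/2). At c = 20% the share after D90 is (0.894 − 0.8)/0.2 = 47%, and the SE ratio is √(0.894/0.8) = 1.06. At c = 40% the share is (0.775 − 0.6)/0.4 = 44%, and the SE ratio is √(0.775/0.6) = 1.14. For rare events, the early-to-late rate ratio at which the share drops to half is (360 − D)/D: 3.0 for D90, 2.5 for D104 and 1.7 for D135.

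**The case against.** The strongest reply is that little depends on this. Per-protocol is a sensitivity analysis in an exploratory trial whose primary results are descriptive. The mITT analysis uses all available visits and is untouched. The SAP also plans ITT, in-window, multiple-imputation and reinfection-censored analyses. All of that stands, and it limits the consequence.

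Four stronger readings are tempting and are not supported.

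- A reader might infer that most exclusions would in fact discard valid D90 data. The documents give no rate or timing. That statement needs roughly even timing and fails if events cluster early enough.
- A reader might infer that SAP 3.1 and SAP 3.8 contradict each other. They are different sensitivity analyses with different triggers and can coexist. SAP 3.8 covers reinfection only. It shows that visit-level exclusion is already accepted in this plan, but it does not reach antiviral or non-study antibody use outside a reinfection.
- A reader might infer that disagreement between per-protocol and mITT could not be interpreted at all. On the assumptions above the precision cost is modest, so that is too strong.
- A reader might infer that AER002 itself drives the exclusions. Resistant infections are by definition ones it is not expected to neutralize, and treatment is blinded. Some effect on antiviral use is possible, but the documents offer no evidence of it.

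It is also fair to say that no explicit end date is given for the exclusions. D360 is the natural reading of a rule covering the trial. The acute-illness item has no reference date, so a whole-trial reading cannot be shown for it.

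**Conclusion.** The point holds as a defect in a secondary analysis. For non-study antibody, resistant infection and COVID antivirals, the rule removes D90 scores recorded before the event and selects the D90 set on later events. That follows from the wording and needs no assumed rate.

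The size does rest on assumptions. With a constant rate, equal in both arms, and 20% to 40% incidence by D360, about 70% to 73% of excluding events fall after D90, and the D90 per-protocol standard error is about 9% to 21% larger than needed. Measured from the end of the extended window, 54% to 61% of events fall later (10% to 50% incidence). With an early rate three times the late rate, under half fall after D90 and the inflation is about 6% to 14%. The primary mITT result does not change in any of these cases.

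**What to change.** In SAP 3.1, define per-protocol by timepoint. Exclude a participant's visits from the date of the non-study antibody, resistant infection or COVID antiviral onward, and keep all earlier visits. Compare the event date with the actual date of the assessment, so that visits in the extended window are handled correctly. The D90 per-protocol analysis then excludes only participants with an event before their own D90 assessment, and the same rule serves the other visits. Tie recent acute illness to the visit being analysed, with a stated interval.

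The cost is SAP wording; protocol 15 already lets the SAP carry changes to the analysis plan. No new data collection is needed: concomitant medications are reviewed at every visit (protocol Appendix 1), and medication and adverse-event dates are captured (protocol 9.1.1 and 9.1.7).

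There are limits. Medication dates may be estimated, so the SAP should say how an uncertain date close to a visit is treated. Genotyping is optional (protocol 9.3.5), so resistance may be unknown for some infections; that difficulty exists under the current rule too. Selection from events before D90 remains, so the revised analysis is still a sensitivity analysis.

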#### **3.2. Descriptive statistics**

Descriptive statistics will be reported overall and by randomization group. For categorical outcomes, the number and percent in each category will be reported; percentages will be of non-missing values, if data are not complete. Continuous variables will be summarized by median (interquartile range [IQR]) and/or mean (SD). Continuous variables may be categorized (e.g., age may be broken into categories to investigate the distribution across age groups).

### **3.3. Binary outcomes**

For binary outcomes, probabilities will be compared between the investigational agent and its control group using Fisher's exact tests or logistic regression. Proportions will be accompanied by Agresti Coull 95% confidence intervals. Relative risks will be calculated with 2-sided 95% confidence intervals. Risk difference (RD) with 2-sided 95% confidence intervals (CI) will also be compared between the groups. If the numbers in the denominators are small, our confidence intervals will use the pseudo-observation approach of Agresti and Caffo.

For longitudinally measured binary outcomes, the treatment effect, in relative risks, through follow-up will be estimated with 95% confidence intervals using generalized estimating equations (GEE) with a Poisson family and a log link function; the treatment effect is estimated via the interaction between the indicator for randomization group and the binary indicator for follow-up (versus baseline) visits. Here, we may also employ the pseudo-observation approach to calculating the confidence intervals if the outcomes are rare. The treatment effect, in risk differences, with 95% confidence intervals will be estimated by marginalizing the models and calculating 95% confidence intervals by the chain rule.

### **3.4. Ordered categorical outcomes**

Ordinal variables will be compared between randomization groups using Wilcoxon-Mann-Whitney. We may summarize effects quantifying the treatment effects using the proportional odds model with the summary OR of being in a better category in the AER002 group compared to the placebo group, adjusted for baseline category, will be estimated with a 2-sided 95% CI. The validity of the proportional odds assumption will be assessed by testing the log ORs (for the treatment effect) across the dichotomized cumulative ordered categories in the corresponding ordered logistic regression model (partial proportional odds model, test for "unequal slopes"). For longitudinal measured ordinal variables, the treatment effect through follow-up will be estimated with 95% confidence intervals using generalized estimating equations (GEE) with a logistic link function; the treatment effect is estimated via the interaction between the indicator for randomization group and the binary indicator for follow-up (versus baseline) visits.

### **3.5. Continuous outcomes**

Continuous outcomes will be compared between randomization groups using ANCOVA models for comparing means, if the ANCOVA model assumptions hold. If the distributions of the continuous outcomes are skewed, outcomes may be transformed or compared between randomization groups using rank-based methods, such as the Wilcoxon test, or quantile (median) regression. For example, biomarker levels often require log-transformation to meet model assumptions for ANCOVA analyses.

Comparisons between randomization groups for a continuous outcome will be adjusted for baseline values of the outcome, for the purpose of variance reduction, unless there are concerns over model stability with such an adjustment.

To estimate the treatment effect for *longitudinally measured continuous outcomes*, including those measured at baseline and just once post-baseline. We will use linear mixed effects models (in case of Gaussian responses) with an indicator for randomization group, visit and visit by group interaction. The model will include an unstructured covariance structure. Models will be adjusted for the baseline values of the outcome variable. As needed, continuous outcomes may be transformed to fulfil the model assumptions (e.g., log-transformation). The estimand will be defined as net “change from baseline” (difference at follow-up visit minus baseline value). The treatment effect through follow-up will then be estimated with 95% confidence intervals

### 3.6. Visit Windows, Interim Visit and Mistimed Visits

Visits will be categorized using the schema below by the Clinical Research Coordinators (CRC) of the study. Not every visit will have taken place on the Target Day, and acceptable visit windows (in days) are shown below.

Visit	Screen	Baseline	Interven t ion	Phone FU	2W	1M	3M	6M	12M
Target Day	-28	-7	0	1	15	30	90	180	360
Visit Window (days)	-28 to -8	-21 to -1	N/A	+1	+/-3	+/-5	+/-14	+/-14	+/-28

We will also group visits by defining an extended window around visit target dates. The windows will be the dates which are mid-way between the target visit dates. For instance, if a person makes a visit at 8 months, this will fall in the period extended window for a 6 month visit which spans from 4.5 months  $\{4.5 = (3+6)/2\}$  to 9 months  $\{9 = (6+12)/2\}$ . The extended visit window for the 12 months would extend to up to 15 months. If there is more than 1 visit in an extended window, then the closer would to the target date will be used. Hence, a visit out of the desired window defined in the table is not excluded.

We will perform a sensitivity analysis which will include only visits which fall in the visit window.

### **3.7. Missing Values**

Our primary analysis will use the available visits without adjustment for missing values.

We will conduct sensitivity analyses will use chained equations to multiply impute missing outcomes data. To this end, we will use the available panel of the measures, demographics and values of other available similar measures.

### **3.8. Intercurrent Events**

Our analysis may be affected by SARS-CoV-2 reinfections during the study period. Our primary analysis will include all visits during the study period. We will perform sensitivity analyses which exclude any visits after a documented or suspected on study reinfections.

### **3.9. Subgroup analyses**

We will perform subgroups analyses by participant sex and antigen detection at baseline. A subgroup effect will be tested by a two-sided 0.05 level test of interaction.

## **4. Efficacy Analyses**

The primary efficacy analyses will be conducted in the mITT population. Analysis in the per protocol population will be considered a sensitivity analysis.

### **4.1. Primary Efficacy Outcome**

The primary efficacy outcome is the change in PROMIS-29 Physical Health summary score from Baseline to D90. This will be analyzed from the mITT population using a linear regression model for follow-up PROMIS-29 with terms for the baseline value, randomized treatment – an analysis of covariance model (ANCOVA).

The significance of the treatment comparison will be given by a two-sided 0.05 level test for the randomized treatment term.

The mean PROMIS-29 Physical Health summary score to D90 can be calculated by marginalizing the ANCOVA model above.

Note, these estimates will differ from both taking the mean PROMIS-29 at the baseline and D90 timepoints. However, the ANCOVA estimate is more efficient.

### **4.2. Secondary Efficacy Analyses**

Secondary efficacy outcome will be analyzed from the mITT population. There will be no formal adjustment for multiple testing in analyzing the secondary endpoints. Secondary outcomes are listed in [4.2.1](#), [4.2.2](#) and [4.2.3](#).

#### 4.2.1 Questionnaires

- Change in PROMIS-29 Physical Health summary score from Baseline to D30 and D180.
  - The primary estimand for this outcome is the difference in mean PROMIS-29 Physical Health summary score from baseline.
  - This continuous outcome will be analyzed as described in [Section 3.5](#), i.e. using a mixed effect model for repeated measurements.
- Change in PROMIS-29 Mental Health summary score from Baseline to D90.
  - The primary estimand for this outcome is the difference in mean PROMIS-29 Mental Health summary score from baseline.
  - This continuous outcome will be analyzed as described in [Section 3.5](#), i.e. using a mixed effect model for repeated measurements.
- Change in PROMIS-29 Mental Health summary score from Baseline to D30 and D180.
  - The primary estimand for this outcome is the difference in mean PROMIS-29 Mental Health summary score from baseline.
  - This continuous outcome will be analyzed as described in [Section 3.5](#), i.e. using a mixed effect model for repeated measurements.
- LIINC Questionnaire – Quality of Life at D90 by Visual Analogue Scale (VAS)
  - The primary estimand for this outcome is the difference in mean VASs core from baseline. The baseline value for the analysis will be the mean of screening and day 0 values.
  - This continuous outcome will be analyzed as described in [Section 3.5](#), i.e. using a mixed effect model for repeated measurements.
- Quality of Life Using the 5-Item EuroQol EQ-5D-5L index value score at D90
  - The primary estimand for this outcome is the difference in mean the EQ-5D-5L index value from baseline. The baseline value for the analysis will be the mean of screening and day 0 values.
  - This continuous outcome will be analyzed as described in [Section 3.5](#), i.e. using a mixed effect model for repeated measurements.
- Change in Duke Activity Status Index (DASI) from Baseline to D90

- The primary estimand for this outcome is the difference in mean DASI total score from baseline.
- This continuous outcome will be analyzed as described in [Section 3.5](#), i.e. using a mixed effect model for repeated measurements.
- Change in the Composite Autonomic Symptom Score (COMPASS)-31 from Baseline to D90
  - The primary estimand for this outcome is the difference in mean COMPASS-31 score from baseline.
  - This continuous outcome will be analyzed as described in [Section 3.5](#), i.e. using a mixed effect model for repeated measurements.
- Change in the World Health Organization Disability Assessment Schedule 2.0 (WHO-DAS 2.0) questionnaire from Baseline to D90
  - The primary estimand for this outcome is the difference in mean WHO-DAS 2.0 score from baseline. The baseline value for the analysis will be the mean of screening and day 0 values.
  - This continuous outcome will be analyzed as described in [Section 3.5](#), i.e. using a mixed effect model for repeated measurements.
- Patient Global Impression of Change (PGIC) at D90
  - The primary estimand for this outcome is the relative odds of better change on the PGIC at D90 between the arms.
  - This ordinal outcome will be analyzed as described in [Section 3.4](#).
- Change in the Everyday Cognition Form (ECog-39) instrument from Baseline to D90
  - The primary estimand for this outcome is the difference in mean ECog-39 score from baseline.
  - This continuous outcome will be analyzed as described in [Section 3.5](#), i.e. using a mixed effect model for repeated measurements.

